7.13. Discontinuation of the trial

The trial will be discontinued in the event of any of the following:

- New scientific information is published to indicate that volunteers in the trial are being exposed to undue risks as a result of administration of the IMPs, or as a result of the trial procedures or follow-up schedule.
- Serious concerns about the safety of either of the IMPs arise as a result of one or more IMP-related SAE(s) occurring in the volunteers enrolled in this or any other ongoing trial of these IMPs.
- For any other reason at the discretion of the Investigator.

7.14. End of Study Definition

The trial will be completed when the last volunteer enrolled into the trial has completed their final follow up visit.

8. CLINICAL PROCEDURES

This section describes the clinical procedures for evaluating study volunteers and follow-up after administration of study vaccine.

8.1. Schedule of Attendance

All volunteers will have the same schedule of clinic attendances and procedures as indicated in the Schedules of Visits and Procedures (section 3). The total volume of blood donated during the study will be 160mL. Additional visits or procedures may be performed at the discretion of the investigators, e.g., further medical history and physical examination, or urine microscopy in the event of positive urinalysis. Participants will be given the option of having follow up visits done at school as detailed in section 7.9.

8.2. Observations

Pulse, blood pressure and temperature will be measured at the time-points indicated in the Schedule of Visits and Procedures (section 3) and may also be measured as part of a physical examination if indicated at other time-points.

8.3. Blood tests, urine and stool analysis

Blood will be drawn for the following laboratory tests and processed at the EMaBS clinic laboratory, or in laboratories at the Uganda Virus Research Institute (UVRI), using standard procedures:

- **Haematology and haemoparasitology:** full blood count, malaria slide, *Mansoniella perstans* (using modified Knott's method [59]); malaria PCR will be conducted for sub-microscopic parasitaemia.

- **Biochemistry:** Sodium, Potassium, Urea, Creatinine, Albumin, Liver Function Tests (ALT, ALP, GGT)
- **Diagnostic serology:** HBsAg, HCV antibodies, HIV antibodies (specific consent will be gained prior to testing blood for these blood-borne viruses)
- **Exploratory Immunology:** Immunogenicity will be assessed by a variety of immunological assays. This includes *ex vivo* ELISpot assays for interferon gamma and flow cytometry assay. Other exploratory immunological assays including cytokine analysis and gene expression studies amongst others may be performed at the discretion of the Investigators. Immunological assays will be conducted according to local SOPs.
- **Urinalysis:** Urine will be tested for protein, blood and glucose at screening. For female volunteers only, urine will be tested for beta-human chorionic gonadotropin (β -HCG) at screening and immediately prior to vaccination. Urine will also be examined for circulating cathodic antigen of *Schistosoma* species.
- **Stool:** stool samples will be examined for helminths by the Kato Katz method, and by PCR [60]. A sample will be stored for possible analysis of the microbiome in future.

Genetic studies, including a genome wide association analysis and work on HLA typing, have already been undertaken among EMaBS participants, based on prior ethical approval and consent. Genetic analyses relevant to vaccine responses were the primary motivation for the work. This will provide the opportunity for genetic analyses using immunological data generated under this new protocol also.

Collaboration with other specialist laboratories in the UK, Europe and outside of Europe for further exploratory tests may occur. This would involve the transfer of serum, urine or plasma and/or PBMC to these laboratories, but these would remain anonymised. Informed consent for this will be gained from volunteers. A Material Transfer Agreement will be submitted for review and approval before any samples are sent to collaborating institutions.

8.4. Study visits

The study visits and procedures will be undertaken by one of the clinical trials team. The procedures to be included in each visit are documented in the Schedule of Visits and Procedures (Section 3). Each visit is assigned a time-point and a window period, within which the visit will be conducted.

8.4.1. Screening visit

All potential volunteers will have a screening visit, which may take place up to 120 days prior to vaccination. Informed consent will be taken before screening, as described in section 7. If consent is obtained, the procedures indicated in the Schedule of Visits and Procedures (section 3) will be undertaken including a medical history, physical examination and blood tests.

The subject's EMaBS study file will be reviewed to ascertain any significant medical history. Abnormal clinical findings from the urinalysis or blood tests at screening will be assessed according to normal ranges defined locally by Lugada and colleagues for haematology [61], and those provided by the ISO accredited Clinical Diagnostic Laboratory at UVRI for biochemistry. Any abnormal test result deemed clinically significant may be repeated to ensure it is not a single occurrence. If an abnormal finding is deemed to be clinically significant, the volunteer will be informed and appropriate medical care arranged with the permission of the volunteer.

The eligibility of the volunteer will be reviewed at the end of the screening visit and again when all results from the screening visit have been considered. Decisions to exclude the volunteer from enrolling in the trial or to withdraw a volunteer from the trial will be at the discretion of the Investigator. If eligible, a day 0 visit will be scheduled for the volunteer to receive the vaccine.

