3.2. Schedule of visits and procedures for groups 1-4

Visit number	1	2	3	4	5	6	7
Timeline (days)*	Screening	0	2	14	28	56	168
Timeline (weeks)*		0		2	4	8	24
Time windows (days)	-90 to -7		+1	+3	+5	+5	+14
Vaccination, ChAdOx1 85A		x					
Inclusion/exclusion criteria	x	x					
Review contra-indications	x	x					
Informed consent	x						
Medical history	x	(x)	(x)	(x)	(x)	(x)	(x)
Physical examination	x	(x)	(x)	(x)	(x)	(x)	(x)
Vital signs	x	x	x	x	x	x	x
Urinalysis	x						
β-HCG urine test (female only)	x	x					
Stool parasitology	x	x	x				x
Anthelmintic treatment						x	
Local & systemic events/reactions		x	x	x	x	x	x
Diary cards provided		x					
Diary cards collected				x			
Biochemistry (4mL)**/***	x			x			
HBV, HCV, HIV (6mL)	x						
Haematology: full blood count and storage (2mL)	x		x	x			
Mansonella perstans (1mL)***	x						x
Malaria RDT/slide; PCR (1mL)	x	x***		x	x		x
Assessments of immunogenicity and exploratory immunology incl ELISpot (10-20mL)****	x	x	x	x	x	x	x
Gene expression (2mL)	x		x				
Blood vol (mL)	36	0	6	28	9	5	24
Cumulative blood vol (mL)	36	36	42	70	79	84	108

X Event scheduled to occur

(X) If considered necessary, emphasising any complaint or change in medications

* Timeline is approximate only, as exact timings (\pm windows periods) of visits relate to the actual (not intended) date of the previous visit

** Urea & electrolytes, liver function tests

*** Repeated on vaccination day if delay from screening is more than 28 days

**** Exploratory immunology blood volume will be guided by guidelines from Harvard Mass General, where a maximum of 3ml/kg body weight is taken at any one time point and not more than 3ml/kg is taken over any 8 week period (ref http://www.drgreene.com/21_1616.html.) These guidelines have been followed in previous studies vaccinating adolescents and children with MVA85A (in South Africa [1]). The total blood volume planned is 84 ml over the initial intensive sampling period of 8 weeks. Revision of sample volumes based on weight will only be required for children who weigh less than 28 kg; the average weight of children aged 11 is expected to be greater than 35kg, with greater weights for older children.

Table 1.1. Schedule of trial procedures groups 1-4

Schedule of visits and procedures for groups 5 and 6

Visit number	1	2	3	4	5	6	7	8	9	10
Timeline (days)*	Screening	0	2	14	28	56- 365 ^a	63- 372 ^a	84- 393 ^a	140- 449 ^a	224- 533 ^a

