7.5. Exclusion Criteria

Volunteers must meet none of the following criteria to enter the trial:

- Clinical, radiological, or laboratory evidence of current active TB disease^a
- Laboratory evidence at screening of latent *M.tb* infection as indicated by a positive ELISPOT response to ESAT6 or CFP10 antigens^b
- Previous treatment for active or latent tuberculosis infection
- Shared a residence with an individual who has started on anti-tuberculosis treatment, or been diagnosed with culture or smear-positive pulmonary tuberculosis, within six months prior to day 0
- Received a TST within 90 days prior to day 0

- Clinically significant history of skin disorder, allergy, immunodeficiency (including HIV), cancer, cardiovascular disease, gastrointestinal disease, liver disease, renal disease, endocrine disorder and neurological illness, drug or alcohol abuse
- History of serious psychiatric condition or disorder
- Concurrent oral or systemic steroid medication or the concurrent use of other immunosuppressive agents within 2 months prior to enrolment
- History of anaphylaxis to vaccination or any allergy likely to be exacerbated by any component of the study vaccine, including eggs
- Any abnormality of screening blood or urine tests that is deemed to be clinically significant or that may compromise the safety of the volunteer in the study^a
- Positive HBsAg, HCV or HIV antibodies^a
- Use of an investigational medicinal product or non-registered drug, live vaccine, or medical device other than the study vaccine for 30 days prior to dosing with the study vaccine, or planned use during the study period
- Administration of immunoglobulins and/or any blood products within the three months preceding the planned trial vaccination date
- Female currently lactating, confirmed pregnancy or intention to become pregnant during the trial period
- Screening blood sample positive for malaria by microscopy

^aSubjects who are excluded from the trial because they have been discovered during screening procedures to be suffering from a previously undiagnosed condition thought to require further medical attention will be referred appropriately for further investigation and treatment.

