7.7. Enrolment

Subjects who complete the screening processes, satisfy all the inclusion criteria, and meet none of the exclusion criteria will be enrolled into the trial and their visits scheduled in the calendar. The ongoing eligibility of the subject will be reviewed on the day of enrolment and any new events, medications, or changes to the screening documents recorded. Subjects will be enrolled on the vaccination visit (day 0). The vaccination visit will last approximately two hours, which includes a 60 minute follow up period in the clinic for observation after vaccination.

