7.9. Timepoints

Screening – trial enrolment time window

Enrolment should take place no longer than 90 days following the date of screening appointment. If more than 90 days elapse, the screening visit should be repeated in full prior to enrolment in order to minimise the risk to volunteers of any new unidentified health problems having arisen during that period.

Vaccination of first volunteer – subsequent vaccination time window

The first volunteer, who will be allocated to Group 1, will be vaccinated with ChAdOx1 85A by the intramuscular route at least 7 days before any subsequent volunteers in this group. After safety review by the clinical team and the Chief Investigator of the three Group 1 volunteers, the first volunteer in Group 2 will be vaccinated at least 7 days prior to further volunteer enrolment into Group 2. After similar safety review of the three Group 2 volunteers, the first volunteer in Group 3 will be vaccinated at least 7 days prior to further enrolment into Group 3. After similar safety review of the three Group 3 volunteers, the first volunteer in Group 4 will be vaccinated at least 7 days prior to further enrolment into Group 4. After review by the clinical team and the Chief Investigator of the safety data from groups 1-4, enrolment into the randomised trial will commence. The data and safety monitoring board (DSMB) will be consulted if there are any issues of concern.

Follow up period

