8.4.2. Day 0: Enrolment and vaccination visit

Volunteers will not be considered enrolled in the study until they have received a vaccine. Before vaccination, the eligibility of the volunteer will be reviewed. Pulse, blood pressure and temperature will be observed and if necessary, a medical history and physical examination may be undertaken to determine need to postpone vaccination depending on criteria listed in section 7.11. A pregnancy test will be repeated for female volunteers. Vaccinations will be administered as described below.

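### Section 8.4.1 allows screening up to 120 days before vaccination, against the 90-day limit and full-rescreen rule in section 7.9 and the day -90 to -7 window in Tables 1.1 and 1.2

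*Combined protocol and SAP*

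**What the plan says.** Four places in the current text limit the time from screening to vaccination.

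- Section 8.4.1 (Screening visit): "All potential volunteers will have a screening visit, which may take place up to 120 days prior to vaccination".
- Section 7.9 (Timepoints): "Enrolment should take place no longer than 90 days following the date of screening appointment". It continues: "If more than 90 days elapse, the screening visit should be repeated in full prior to enrolment". The reason given is to guard volunteers against health problems that have arisen undetected since screening.
- Table 1.1 (section 3.2, groups 1-4): screening window day -90 to day -7.
- Table 1.2 (section 3.3, groups 5 and 6): the same window.

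Section 7.7 places enrolment at the day-0 vaccination visit. Section 8.4.2 (Day 0) confirms it: "Volunteers will not be considered enrolled in the study until they have received a vaccine".

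A footnote to both tables governs ageing test results: "Repeated on vaccination day if delay from screening is more than 28 days". Its mark is attached to biochemistry, *Mansonella perstans* and the day-0 malaria test.

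Section 7.5 excludes volunteers for "Positive HBsAg, HCV or HIV antibodies", and for latent *M.tb* infection found at screening "as indicated by a positive ELISPOT response to ESAT6 or CFP10 antigens".

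**The concern.** A screening window fixes how old an eligibility result may be when the vaccine is given. The protocol gives two answers, 90 and 120 days, and attaches a safety rationale only to the shorter one. Staff who follow 8.4.1 may vaccinate at day 110 on the existing screen. Staff who follow 7.9 must rescreen first. A monitor cannot tell from the text whether the first action is compliant or a deviation.

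At stake is the currency of exclusion tests that are not scheduled again before vaccination. HIV status matters most in group 6, where 30 adolescents are to receive BCG: section 5.4.1 itself warns of disseminated disease after BCG in immunocompromised people.

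The situation is plausible in this trial. Section 7.9 describes a COVID-19 halt of nearly three months followed by new enrolment, so someone screened before the halt and vaccinated after it could fall between days 91 and 120. The documents do not say that this happened.

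**Working it through.** No power or sample-size formula applies. The check compares stated limits and then asks which results would be refreshed in the disputed band.

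**Step 1: is it the same interval?** Section 7.9 counts from screening to enrolment, and 8.4.1 from screening to vaccination. Sections 7.7 and 8.4.2 (Day 0) make enrolment and vaccination the same event on day 0. Both limits therefore run between the same two dates.

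**Step 2: the limits side by side.**

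| Place | Longest interval, screening to vaccination |
|---|---|
| 8.4.1 Screening visit | 120 days |
| 7.9 Timepoints | 90 days, then full rescreen |
| Table 1.1 (groups 1-4) | 90 days |
| Table 1.2 (groups 5 and 6) | 90 days |

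One place disagrees with three. Section 8.4 adds that each visit is to take place inside its assigned window, which supports the tables.

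**Step 3: is the 120 superseded?** The amendment history lists no change to the screening window. All four statements are current.

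**Step 4: size of the gap.** 120 - 90 = 30 days, which is days 91 to 120 inclusive. As a proportion of the limit, 30/90 = 33%.

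**Step 5: what is refreshed for a volunteer in the band?** Everyone there has passed the 28-day trigger, by 91 - 28 = 63 to 120 - 28 = 92 days.

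- Repeated under the footnote: biochemistry, *Mansonella*, malaria.
- Also done on day 0: review of eligibility and contraindications, vital signs, urine pregnancy test, stool parasitology.
- Scheduled at screening but not on day 0: HIV, hepatitis B and hepatitis C serology, full blood count, urinalysis.
- Latent TB: both tables mark an immunogenicity row that includes ELISpot on day 0. They do not say that it covers ESAT6 or CFP10, or that a result is read before vaccination. Table 1.1 allots 0 mL of blood on day 0 and Table 1.2 allots 10 mL. No eligibility repeat is stated.

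**Step 6: how many volunteers?** The ceiling is the planned total, 4 × 3 + 2 × 30 = 72. The number screened more than 90 days before vaccination is not given, so the actual count is unknown.

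**The case against.** The strongest reply is that the texts can be read together. Section 8.4.1 is permissive and does not waive the rescreen. A volunteer first seen at day -110 and fully rescreened before day 0 would satisfy both sections. With the tables and section 8.4 on the side of 90 days, most sites would probably treat 120 as a stray number. That is a fair forecast of practice, but it does not rescue the text. Once the rescreen takes place it becomes the operative screening visit, and the 120-day allowance has no function.

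Several narrower points stand:

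- The 90-day design is clear and justified. This is an internal inconsistency, not a poor scientific choice.
- Day 0 gives partial protection. Eligibility is reviewed, new events and medications are recorded, and the household TB exposure criterion is dated to day 0.
- The tables do not prove that ESAT6 and CFP10 are absent from the day-0 ELISpot. They only fail to specify an eligibility repeat.
- Seventy-two is a ceiling. By this version groups 1-4 and some of groups 5 and 6 had been vaccinated, so a text correction protects only those still to be vaccinated.
- The documents give no incidence for the infections concerned, so the added risk from up to 30 days cannot be quantified.

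These points limit the consequence; they do not remove the contradiction.

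**Conclusion.** The concern holds. Section 8.4.1 permits an interval up to 30 days (33%) longer than section 7.9 and both schedule tables allow, and nothing in the documents explains the difference. Followed as written, it would let volunteers be vaccinated on HIV, hepatitis B, hepatitis C and latent-TB results older than the protocol's own safety limit.

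The conclusion rests on two readings: that enrolment and vaccination are the same day, which sections 7.7 and 8.4.2 state, and that the day-0 ELISpot is not an eligibility repeat, which follows from the absence of any such instruction. The serology point does not depend on the second reading. Endpoints, power and the planned analysis are unaffected. This should be corrected because it is an operative eligibility limit, but it does not threaten the trial's conclusions.

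**What to change.** In section 8.4.1 (Screening visit), change the limit from 120 to 90 days and add a sentence such as: *When vaccination would fall more than 90 days after screening, a complete new screening visit is required first (see section 7.9).* Leave section 7.9 and Tables 1.1 and 1.2 as they are.

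For volunteers already vaccinated, compare screening and vaccination dates and document as a deviation any interval over 90 days without a full rescreen.

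The cost is one number and one cross-reference, a check of dates already on file, and a repeat screening visit for anyone still unvaccinated past day 90. The documents do not say how many that would be; few would be expected.

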8.4.2. Day 0: Enrolment and vaccination visit

Volunteers will not be considered enrolled in the study until they have received a vaccine. Before vaccination, the eligibility of the volunteer will be reviewed. Pulse, blood pressure and temperature will be observed and if necessary, a medical history and physical examination may be undertaken to determine need to postpone vaccination depending on criteria listed in section 7.11. A pregnancy test will be repeated for female volunteers. Vaccinations will be administered as described below.

8.4.3. Vaccination (D0)

Group 1 adults will be given ChAdOx1 85A at 5×10^9 vp intramuscularly

Group 2 adults will be given ChAdOx1 85A at 2.5×10^{10} vp intramuscularly

Group 3 adolescents will be given ChAdOx1 85A at 5×10^9 vp intramuscularly

Group 4 adolescents will be given ChAdOx1 85A at 2.5×10^{10} vp intramuscularly

Group 5 adolescents will be given ChAdOx1 85A at 2.5×10^{10} vp intramuscularly followed by MVA85A boost at 1×10^8 pfu intramuscularly between day 56 and day 140

Group 6 adolescents will be given BCG revaccination, Serum Institute of India, 0.1 mL intradermally

Following vaccination the following procedures will be undertaken:

In all groups, volunteers will be given a thermometer, tape measure and paper diary card, with instructions on use, along with the emergency 24 hour telephone number to contact the on-call study physician if needed. Volunteers will be instructed on how to self-assess the severity of these AEs. There will also be space on the diary card to self-document unsolicited AEs, and whether medication was taken to relieve the symptoms. Diary cards will collect information on the timing and severity of the following solicited AEs:

Local solicited AEs	Systemic solicited AEs
Pain	Fever
Redness	Feverishness/Chills
Warmth	Joint pains
Itch	Muscle pains
Blistering or ulceration	Fatigue
Swelling of local lymph nodes	Headache
	Malaise
	Abdominal pain
	Chills

Table 6. Solicited AEs as collected on post vaccination diary cards

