10.1.1. Holding criteria

Safety holding rules would be activated by any of the following:

- **A serious adverse event considered possibly, probably or definitely related to vaccination occurs**
- **Death occurs**
- **A life-threatening reaction occurs**
- **Solicited systemic adverse events:**

If 2 or more vaccinations in group 1, 2, 3 or 4; or more than 25% of doses of the vaccine in group 5; is followed by the same Grade 3 solicited systemic adverse event beginning within 2 days after vaccination (day of vaccination and one subsequent day) and persisting at Grade 3 for >48hrs.

- **Unsolicited adverse events:**

If 2 or more vaccinations in group 1, 2, 3 or 4; or more than 25% of doses of the vaccine in group 5; develop the same Grade 3 unsolicited adverse event beginning within 7 days after vaccination that is considered related to vaccination and persists at Grade 3 for > 48 hours.

- **Laboratory adverse event:**

If 2 or more vaccinations in group 1, 2, 3 or 4; or more than 25% of doses of the vaccine in group 5; develop the same Grade 3 laboratory adverse event beginning within 7 days after vaccination and persists at Grade 3 for > 48 hours.

If a holding rule has been met, the internal safety review will consider:

- The relationship of the AE or SAE to the vaccine.
- The relationship of the AE or SAE to the vaccine dose, or other possible causes of the event.
- If appropriate, additional screening or laboratory testing for other volunteers to identify those who may develop similar symptoms and alterations to the current Volunteer Information Sheet (PIS).
- New, relevant safety information from ongoing research programs on the various components of the vaccine.

The local ethics committee and vaccine manufacturers will also be notified if a holding rule is activated or released.

All vaccinated volunteers will be followed for safety until the end of their planned participation in the study or until resolution or stabilisation (if determined to be chronic sequelae) of their AEs, providing they consent to this.

In addition to these pre-defined criteria, the study can be put on hold upon advice of the Chief Investigator, Principal Investigator, Study Sponsor, Regulatory Authority, Ethical Committee(s) or DSMB, for any single event or combination of multiple events which, in their professional opinion, jeopardise the safety of the volunteers or the reliability of the data.

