10.5. Reporting Procedures for All Adverse Events

All local and systemic AEs occurring in the 28 days following each vaccination observed by the Investigator or reported by the volunteer, whether or not attributed to study medication, will be recorded. Recording and reporting of all AEs will take place as detailed in the study's SOP. All AEs that result in a volunteer's withdrawal from the study will be followed up until a satisfactory resolution occurs, or until a non-study related causality is assigned (if the volunteer consents to this). Serious adverse events (SAEs) will be collected throughout the entire trial period.

Adverse event	
Local	Pain/tenderness at the injection site
	Swelling at injection site
	Warmth at the injection site
	Itch at the injection site
	Scaling/pustules at the injection site
Systemic	Documented fever (temperature > 37.5° C)
	Myalgia
	Arthralgia
	Feverishness
	Headache
	Fatigue
	Nausea
	Malaise

Table 8. Routinely solicited adverse events

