10.6. Assessment of Severity

The severity of clinical and clinical laboratory adverse events will be assessed according to the scales in Table 9-11. Clinical laboratory adverse events will be assessed as grade 1 if 1.1 to 2.4 times the limit of normal, grade 2 if 2.5 to 4.9 times, and 3 if greater than 5 times the limit of normal, in accordance with FDA guidance for toxicity grading. Normal ranges will be based on those defined locally by Lugada and colleagues for haematology [61], and those provided by the ISO accredited Clinical Diagnostic Laboratory at UVRI for biochemistry.

Adverse Event	Grade	Intensity
Pain at injection site	1	Pain that is easily tolerated
	2	Pain that interferes with daily activity
	3	Pain that prevents daily activity
Erythema at injection site*	1	>3 - ≤50 mm
	2	>50 - ≤100 mm

	3	>100 mm
Swelling at injection site	1	>1 - ≤20 mm
	2	>20 - ≤50 mm
	3	>50 mm

Table 9. Severity grading criteria for local adverse events

*erythema ≤3mm is an expected consequence of skin puncture and will therefore not be considered an adverse event

	Grade 1 (mild)	Grade 2 (moderate)	Grade 3 (severe)
Fever	37.6°C - 38.0°C	38.1°C – 39.0°C	>39.0°C
Tachycardia (bpm)*	101 - 115	116 – 130	>130
Bradycardia (bpm)**	50 – 54	40 – 49	<40
Systolic hypertension (mmHg)	141 - 159	160 – 179	≥180
Diastolic hypertension (mmHg)	91 - 99	100 – 109	≥110
Systolic hypotension (mmHg)***	85 - 89	80 – 84	<80

Table 10. Severity grading criteria for physical observations [appropriate adjustments will be made for age, gender and height percentiles]

*Taken after ≥10 minutes at rest; **When resting heart rate is between 60 – 100 beats per minute. Use clinical judgement when characterising bradycardia among some healthy volunteer populations, for example, conditioned athletes; ***Only if symptomatic (e.g. dizzy/ light-headed)

GRADE 0	None
GRADE 1	Mild: Transient or mild discomfort (< 48 hours); no medical intervention/therapy required
GRADE 2	Moderate: Mild to moderate limitation in activity – some assistance may be needed; no or minimal medical intervention/therapy required
GRADE 3	Severe: Marked limitation in activity, some assistance usually required; medical intervention/therapy required, hospitalisation possible

Table 11. Severity grading criteria for respiratory and systemic AEs

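### The diary-card list (Table 6) and the routinely solicited list (Table 8) conflict: injection-site swelling and nausea are not prompted on the card, and the applicable holding rule depends on which list governs

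*Combined protocol and SAP*

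**What the plan says.** Section 8.4.3 states: "Diary cards will collect information on the timing and severity of the following solicited AEs". The list that follows is captioned "Table 6. Solicited AEs as collected on post vaccination diary cards". It has six local lines (pain, redness, warmth, itch, blistering or ulceration, lymph-node swelling) and nine systemic lines (fever, feverishness/chills, joint pains, muscle pains, fatigue, headache, malaise, abdominal pain, chills). Its only swelling line is "Swelling of local lymph nodes". Volunteers also receive a thermometer and a tape measure, and the section adds: "There will also be space on the diary card to self-document unsolicited AEs".

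Section 10.5 has a second list, "Table 8. Routinely solicited adverse events". It has five local terms (pain/tenderness, swelling, warmth, itch, scaling/pustules) and eight systemic terms (documented fever, myalgia, arthralgia, feverishness, headache, fatigue, nausea, malaise).

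Table 9 in section 10.6 gives severity scales for three local events only: pain, erythema and "Swelling at injection site", the last two in millimetres. Section 5.4.1 names swelling among the typical local reactions to intramuscular injection.

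Section 10.1.1 sets separate holding rules by class of event. The solicited rule applies when a vaccination "is followed by the same Grade 3 solicited systemic adverse event beginning within 2 days after vaccination"; it covers systemic events only and has no relatedness condition. The unsolicited rule allows onset up to 7 days but requires the event to be considered related to vaccination. Nothing in the protocol says which table defines *solicited*.

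**The concern.** Adverse events are a primary outcome (section 6), and section 11 summarises them by type, frequency, severity and group. A prompted diary line and a volunteer's own free-text entry are not equally sensitive, above all for transient, non-serious reactions in adolescents. If a term has a grading scale but no prompted line, its recorded frequency and peak grade depend on whether the volunteer chooses to write it down and measure it.

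The second issue is operational. The holding rules turn on the word *solicited*, and two current tables give it two meanings. The same Grade 3 event could count towards a hold under one table and not under the other, and the protocol offers no way to decide between them.

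**Working it through.** The plan has no figure to reproduce here. The check is a term-by-term match of the tables, followed by a reading of section 10.1.1 under each list.

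**Step 1: match the lists.** Joint pains are taken as arthralgia, muscle pains as myalgia, and the card's combined feverishness/chills line as feverishness.

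| | In both | Table 6 (diary) only | Table 8 only |
|---|---|---|---|
| Local | pain, warmth, itch (3) | redness, blistering/ulceration, lymph-node swelling | injection-site swelling, scaling/pustules |
| Systemic | fever, feverishness, arthralgia, myalgia, fatigue, headache, malaise (7) | abdominal pain, second chills line | nausea |

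Table 8 has 5 + 8 = 13 terms, of which 3 + 7 = 10 are on the card, leaving 3 without a prompted line. Table 6 has 6 + 9 = 15 lines, leaving 15 − 10 = 5 outside Table 8: four distinct terms and the duplicate chills. If scaling/pustules and blistering/ulceration are treated as one term, the 3 becomes 2 and the four become three.

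**Step 2: compare with Table 9.** Of the three graded local events, only pain is in both lists. Erythema (redness) is on the card but not in Table 8. Injection-site swelling is in Table 8 but not on the card.

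**Step 3: what else can capture swelling and nausea.** After the prime, the Table 1.2 visits fall on days 2, 14 and 28. After the boost, the next visits are at 7 and 28 days, with no day-2 visit. Physical examination after screening is marked as done only if considered necessary. A swelling that peaks and resolves in the first week after the boost may therefore have no contemporaneous measurement unless the volunteer writes one in.

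**Step 4: apply section 10.1.1 literally under each list.** All events below are Grade 3 and persist beyond 48 hours.

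| Event | If Table 6 defines solicited | If Table 8 defines solicited |
|---|---|---|
| Nausea, onset day 1, judged unrelated | unsolicited; does not count | solicited systemic; counts |
| Nausea, onset day 5, judged related | unsolicited; counts | solicited systemic; outside the window |
| Nausea, onset day 1, judged related | counts | counts |
| Abdominal pain, onset day 1, judged unrelated | solicited systemic; counts | unsolicited; does not count |
| Abdominal pain, onset day 5, judged related | solicited systemic; outside the window | unsolicited; counts |
| Injection-site swelling, onset within 7 days, judged related | unsolicited; counts | solicited local; no category-specific rule |

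**Step 5: threshold.** It is the same for both classes. In groups 1 to 4 it is two or more vaccinations, with three volunteers per group, so the classification of one event can decide whether the rule is met. In group 5 it is more than 25% of doses: 0.25 × 30 = 7.5, so at least 8 of 30 if each vaccine is counted alone, or 0.25 × 60 = 15, so at least 16 of 60 if both doses are pooled. The text does not say which.

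**The case against.** The best defence is that nothing is lost. The card has free-text space, volunteers hold a tape measure and an emergency number, reactions are assessed at every visit from day 0, and section 10.5 records all adverse events for 28 days after each vaccination, whether observed or reported. The primary safety outcome is all adverse events, with no split between solicited and unsolicited. The holding rules share a severity grade, a persistence requirement and a count threshold; an event that starts early and is judged related counts for nausea and abdominal pain under either list; and section 10.1.1 also lets the investigators, sponsor, regulators, ethics committees or DSMB advise a hold for other events.

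Most of that stands, and it rules out three stronger readings that a reader might infer:

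- *That swelling and nausea are missed, or seen only at visits.* Free text contradicts this. Nor can one say that they lose daily capture, since the protocol states no daily frequency for any diary item.
- *That their frequency and grade are understated.* The documents support a risk of under-recording, not a known bias.
- *That every mismatched term moves between the two holding rules.* The solicited rule is confined to systemic events, so only nausea and abdominal pain can move between the two windows. For swelling, the contrast is between the unsolicited rule and no category-specific rule.

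What the defence does not remove is the conflict itself. Both tables are current text and appear complete, and a discretionary hold does not settle how a predefined rule should be read.

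**Conclusion.** The two solicited lists conflict, and the point holds at the level of something the sponsor should correct. Three of 13 Table 8 terms lack a prompted diary line (two if scaling/pustules is equated with blistering/ulceration), and four diary terms are absent from Table 8 (three on that same reading). The most consequential gap is injection-site swelling: graded in millimetres and named as a typical reaction, but unprompted, so its frequency and peak grade may be under-recorded, especially after the boost. On the holding rules, the ambiguity matters for nausea and abdominal pain when onset is early and the event is judged unrelated, or when onset is later and it is judged related. It also matters for Grade 3 injection-site swelling. No power or immunogenicity figure is affected.

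This rests on the tables as printed. Section 10.5 defers recording detail to an SOP that is not among the documents; the printed card or that SOP may already resolve part of the mismatch, but the protocol does not.

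**What to change.** Reconcile Tables 6, 8 and 9 into one solicited list, so that every event the protocol both solicits and grades has a prompted diary line, including injection-site swelling in millimetres. Remove the duplicate chills entry, and say whether scaling/pustules and blistering/ulceration are one term or two. Reconcile section 10.1.1 with that list by stating which list defines *solicited*. No threshold need change, and how each event should be handled under the holding rules is for the sponsor and the DSMB to settle.

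For cards already completed, report the mismatched terms separately and label them as not diary-prompted, so that their rates are not read alongside prompted ones.

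The cost is a reprinted card, revised table wording and a small break in comparability with earlier cards, since participants enrolled before the change will have been prompted differently.
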